Amendment 02	31-Jul-2014	The purpose of this amendment is to provide clarification and consistency on various sections in the protocol: for consistency, upper limit of age has been updated in some sections of the protocol to > 18 years old, early decision for dose escalation section has been updated and correction has been made to method of assigning subject identification section. In addition, some typographical edits, format updates and clarifications are made throughout the protocol.
Original Protocol	20-Jun-2014	Not applicable

SYNOPSIS

Clinical Protocol IM140103

Protocol Title: Open Label, Adaptive Design, Ascending, Multiple-Dose Study to Evaluate Safety and Efficacy of BMS-986004 in Adult Subjects with Primary Immune Thrombocytopenia (ITP)

Investigational Product(s), Dose and Mode of Administration, Duration of Treatment with Investigational Product(s): Total of 40 subjects will be enrolled for the study, treated in dose panels of 10 subjects each. Four (4) dose panels are planned to be enrolled sequentially in an ascending manner, with dose intensity selected to provide increased levels of immunosuppression at steady state. Dose levels that are planned to be evaluated in this trial are expected to elicit a range of clinical response. Based on current preclinical projections, the doses range from 75 mg to 1500 mg every two weeks.

BMS-986004 will be administered once every 2 weeks as an IV infusion for a total of 7 doses. Subjects will receive investigational product on Day 1/Week 0, Week 2, Week 4, Week 6, Week 8, Week 10 and Week 12, for a total of 7 doses.

During the long term extension (LTE) period, BMS-986004 will be administered once every 2 weeks as an IV infusion for 24 weeks and during 2 Taper visits.

Study Phase: Phase 1b/2

Research Hypothesis: Because current study is an open label trial without placebo control, there is no formal research hypothesis to be statistically validated. The purpose of this study is to test if BMS-986004 will be effective in normalizing platelet counts in subjects with ITP, as well as to assess the safety, PK and immunogenicity of multiple doses of BMS-986004 in ITP subjects.

Primary Objectives:

- To assess the overall safety and tolerability of multiple doses of BMS-986004, when administered in subjects with chronic ITP.

Secondary objectives:

- To evaluate efficacy of BMS-986004 in the treatment of thrombocytopenia in subjects with chronic ITP, as measured by platelet response/complete response (R/CR) and other clinical parameters.
- To establish BMS-986004 dose response, as measured by platelet count and other clinical parameters.
- To measure the target engagement of BMS-986004 following multiple IV doses
- To assess the effect of BMS-986004 on markers associated with the risk of thromboembolism (TE) in the multiple dose setting
- To assess pharmacokinetics and immunogenicity of multiple doses of BMS-986004 in subjects with chronic ITP

[REDACTED]

[REDACTED]

[REDACTED]

[REDACTED]

Long Term Extension Period Objective:

To assess the long term clinical safety, tolerability and efficacy of BMS-986004.

Study Design: This is a Phase 1b/2, multicenter, open-label study to evaluate the safety, efficacy, dose response, and pharmacology (PK, target engagement and PD) of BMS-986004 in subjects with ITP.

The study will comprise a short-term period and a long-term extension (LTE) period.

The short-term period, is divided into three phases: Response Phase (6 weeks), Remission Phase (6 weeks) and Follow Up phase (8 weeks).

Screening evaluations to determine subject eligibility will be performed 21 days prior to study drug administration. The screening period may exceed 21 days but not more than 42 days total only after a discussion with and approval by the Study Director. If an extension in screening time is granted, the patient must still follow the platelet count rules for enrollment. The baseline platelet count determining enrollment eligibility will be based on the mean of two determinations taken within a week before the first dose. To be eligible for enrollment, platelet count needs to be less than 30,000/mm³ and show stable or declining trend. If the mean platelet count is between 30,000 - 35,000/mm³ the subject may be considered for enrollment on a case by case basis after discussion with and approval by the Study Director.

Following screening, a total of 40 evaluable subjects are planned for the study. Subjects are considered evaluable if they receive the first 4 doses of study drug and complete the required safety and efficacy evaluations at Day 50. Non-evaluable subjects will be replaced to maintain a count of 10 subjects in each dose panels, except subjects will not be replaced if they are discontinued from the study secondary to an adverse event unless the adverse event can be determined to be unrelated to treatment.

Subjects are treated in dose panels of 10 subjects each. Four (4) dose panels are planned to be enrolled sequentially in an ascending manner, with dose intensity selected to provide increased levels of immunosuppression at steady state. Dose levels (range from 75 mg to 1500 mg administered every two weeks) that are planned to be evaluated in this trial are expected to elicit a range of clinical response.

BMS-986004 will be administered once every 2 weeks as an IV infusion for a total of 7 doses. Four (4) doses will be administered during the Response Phase over a 6 week treatment period. The remaining 3 doses will be administered during the Remission Phase of the study over a 6 week treatment period. Subjects will receive investigational product on Day 1/Week 0, Week 2, Week 4, Week 6, Week 8, Week 10 and Week 12, for a total of 7 doses.

Each dose cohort will enroll 10 new subjects, starting with the respective dose level at Day1/Week 0, regardless of the number of subjects joining a dose cohort because of intra-subject dose escalation.

A new cohort may be opened to treat subjects at a dose lower than 75 mg if at least 6 subjects treated at the 75 mg cohort achieve platelet Response (R) (platelet count $\geq 30,000/\text{mm}^3$ and at least 2-fold increase from the baseline count and absence of bleeding), at the end of response phase (Week 6). The new cohort would follow the same schedule as the other cohorts including intra-subject dose escalation.

The **Long-term extension (LTE)** period is optional and will include eligible subjects (defined as subjects from either cohort 3 or cohort 4 who complete 12 weeks (85-days) of treatment and who achieve a response as defined by at least a doubling of platelets from Short Term Day 1 baseline and a platelet count of $\geq 35,000/\text{mm}^3$. If a subject has platelet counts close to a doubling of platelets and/or between 30,000-35,000 platelets/mm³, the subject may be considered for the long term extension on a case by case basis, which will involve a review of data from the short term period and which will require approval by the Study Director.

Intra-subject dose escalation

Intra-subject dose escalation could occur after the subject has completed the Response Phase of the study. Subject will receive the next higher dose of BMS-986004 if clinically significant response has not been achieved based on measurement of platelet count on the last two consecutive counts performed at Day 43 and Day 50, and a favorable

safety profile is observed. Clinically significant response is defined as achieving platelet count $\geq 50,000/\text{mm}^3$ with an increase of at least $20,000/\text{mm}^3$ from baseline and absence of bleeding. Subject will then be dosed at the higher dose level for the remainder of the study (Remission Phase).

Dose frequency adjustment for responders exceeding $450,000/\text{mm}^3$ (for non-splenectomized subjects) and $600,000/\text{mm}^3$ (for splenectomized subjects) platelet count

For both the short-term period and the long-term extension, in the event that platelet count exceeds $450,000/\text{mm}^3$ for non-splenectomized subjects and $600,000/\text{mm}^3$ for subjects who underwent splenectomy, in the absence of recent (administered within two weeks) rescue medication, as indicated by the two consecutive platelet count measurements, dosing of the BMS-986004 should be stopped. Subject will remain in the study and platelet counts will be then assessed based on the normal study visit schedule. Dosing of BMS-986004 could be reinitiated only after discussion between Study Director and Investigator if clinically appropriate and dictated by the medical judgment and subject's safety.

Dose escalation for dose panel and stopping rules

Decisions regarding dose escalation will be made based on the review of all cumulative safety information which includes, in general, the safety data through study Day 15 from the 10 subjects in the preceding lower dose cohort. If neither of the below stopping rules is present in dose panel, then dose escalation may proceed within the next higher dose level. However, escalation to the next higher cohort may occur when none of the stopping rules have been met and no less than 5 subjects in a cohort have been followed for at least 2 weeks under certain conditions as illustrated in the section of early decision of dose escalation for dose panel.

The stopping rules listed below will be used to determine whether it is safe to escalate to the next higher cohort. Dose escalation to the next planned dose will not proceed if any of the following criteria are met (Adverse event grading as defined by the Common Terminology Criteria for Adverse Events [CTCAE, Version 4.0]):

- Five or more subjects in a cohort have platelet counts $>450,000/\text{mm}^3$ for non-splenectomized subjects and $>600,000/\text{mm}^3$ for subjects who underwent splenectomy, and platelet count raise is not attributable to a rescue or concomitant therapy.
- Two or more subjects have serious adverse events in the same organ system (Grade 3 and above), that are determined to be related to study medication
- It is determined that the limit of safety and/or tolerability has been reached. This decision will be made following discussions between the Study Team and the Investigator

If any of the above criteria are met within a dose level, the progression to a higher dose level will be put on hold and all safety data available across the study will be evaluated to estimate the risk of proceeding to the higher dose level. The review will include all of the subject(s) that experienced SAEs listed above. In addition, data set may include subjects from a dose panel, the entire dose panel, or if appropriate, all randomized subjects treated to date.

In addition, decision may be made following discussions between the Study Team and the Investigator to halt dose escalation for reasons not defined above, including but not limited to, observing a single serious adverse event in individual subjects, observing trends in a given dose panel and across dose panels, and/or it is determined that the limit of safety and/or tolerability has been reached.

[figure not shown]
If dose escalation is stopped due to any of these findings, additional cohorts may receive the same or lower doses of the investigational compound.

At the time of dose escalation, dose levels of new cohorts may be adjusted to lower doses if the accumulated safety data so dictates.

Adaptive dose selection may be performed to adjust some pre-selected doses, e.g., the third or/and fourth cohort doses, using accumulated efficacy and dose or exposure data. Models based on response rate, such as but not limited to (Bayesian) logistic regression, (Bayesian) EMax model, may be utilized to predict a dose satisfying certain

efficacy criteria, which might be different from the standard. If there are enough responding subjects with multiple platelet measurements, changes of platelet count may be directly modeled by dose and study day to facilitate dose prediction. The selected dose for a cohort should not exceed the originally planned dose for that cohort, i.e., selected dose for cohort C should not be larger than 675mg and it should be at most 1500mg for cohort D.

Figure 3.1.3-1: Study Design Schematic: Short Term Period

*Will not apply to subjects entering LTE

Figure 3.1.3-2: Study Design Schematic: Short Term Period

[figure not shown]
[figure not shown]

Figure 3.1.3-3: Study Design Schematic: Long term extension period

Early Decision of Dose escalation for dose panel

When a cohort is filled and a new subject is available to be treated, an early decision can be made on whether to open the next higher cohort if not all the subjects have completed the evaluation period. The early decision rule is based on controlling the probability of making a wrong early decision, called decision risk, to be at most 15%. Detailed information on deriving the decision risk is included in [Appendix 1](#).

The early decision rule is based on the largest number of subjects who developed AE of interest which is drug-related SAE within the same organ system at grade 3 or higher. The early decision does not directly take into consideration other criteria as covered by the stopping rule. As such, its decision can be modified upon agreement from both investigators and sponsor. In case subjects are allocated to the higher cohort and at least one stopping rule as stated above is triggered toward the lower dose cohort when more events are observed at the lower cohort, decision will be made upon agreement from both investigators and sponsor after considering all safety data.

Three count numbers are used by the decision rule and are defined as follows.

- Titration-Dose Evaluable Subjects (nH): the number of subjects who are titrated and complete the evaluation period (2 weeks) starting from the first titration dose (on day 43).
- Start-Dose Evaluable Subjects (nL): the number of subjects who develop drug related SAE at grade 3 or higher or complete the evaluation period (2 weeks) from the first dose (on day 1) but haven't completed the 2 weeks evaluation period following the first titration dose (on day 43) if being titrated to a higher dose.

- Subjects with AE of Interest (k): the largest number of subjects who developed drug related SAE within the same organ system at grade 3 or higher, which could happen any time after the first dose of BMS-986004 till the decision making day. The value of k is allowed to be either 0 or 1. Note that it doesn't distinguish at which stage of treatment, prior to or post titration, that such AE happened.

Minimum Requirement for Cohort Escalation

A set of minimum safety requirement, as listed below, must be met in order to make an early decision.

- There must be at least 5 (nL+nH>=5) safety evaluable subjects (with safety data through study Day 15)
- A higher dose than the new cohort's start dose must be shown tolerated in the IM140-002 study.

Early Decision Rule:

If there is not AE of interest observed, the early decision rule is the same as the minimum requirements.

If there is one AE of interest observed, the early decision rule is shown in [Table 3.1.4-1](#), where W represent wait, i.e., not enough evidence to enable dose panel escalation, and E represents escalate.

If there are least two subjects with AE of interest, stopping rule is triggered, and subject cannot be treated at the next higher cohort.

Study Population:

Male and Female subjects ≥ 18 years old with persistent or chronic ITP according to American Society of Hematology (ASH), with or without prior splenectomy guidelines will be eligible to participate in the study.

Women of childbearing potential (WOCBP) must not be nursing or pregnant and must be using an acceptable method of contraception for at least 4 weeks before dosing. WOCBP must have a negative pregnancy test within 24 hours prior to dosing with study medication

Study Drug includes both Investigational [Medicinal] Products (IP/IMP) and Non-investigational [Medicinal] Products (Non-IP/Non-IMP) as listed:

Study Drug for BMS-986004

Medication	Potency	IP/Non-IP
Lyophilized Cake of BMS-986004 for injection, 190 mg/vial	50 mg/mL	IP

Study Assessments:

- Safety Outcome Measures: Safety assessments will be based on medical review of adverse event reports and the results of vital sign measurements, ECGs, physical examinations, and clinical laboratory tests. The incidence of observed adverse events will be tabulated and reviewed for potential significance and clinical importance.
- Efficacy Assessments: Response (R) - platelet count ≥ 30,000/mm³ and at least 2-fold increase from the baseline count and absence of bleeding, or Complete response (CR) - platelet count ≥ 100,000/mm³ and absence of bleeding, or Overall response rate (ORR) defined as the proportion of subjects who achieved a CR or R.
- Pharmacokinetic Measures: Pharmacokinetic parameters (Cmax, Ctrough), will be derived from serum concentration versus time
- Biomarker Measures: CD40L receptor occupancy and free soluble CD40L will be measured to determine target engagement. Total soluble CD40L will be measured as a potential PD biomarker. Platelet-associated anti-

platelet antibody titers will be measured to explore possible effects on the primary pathogenic disease mechanism in ITP. Whole genome RNA profiling in the peripheral blood will be undertaken to explore CD40 pathway activation and to enumerate plasmablasts by gene expression. Peripheral blood mononuclear cells (PBMCs) will be purified from whole blood and analyzed by flow cytometry to determine if baseline leukocyte phenotypes inform on patient response to therapy and/or if leukocyte phenotypes are affected by drug therapy. Plasma molecules that may be associated with the disease or drug target pathway, including cytokines and chemokines, will be measured. The primary safety biomarkers, d-Dimer and Thrombin anti-Thrombin (TAT), will be monitored to evaluate risk of thromboembolism. Exploratory safety biomarkers to monitor possible effects on protective immunity will include immune cell enumeration by T, B, NK TruCount and phenotyping by flow cytometry.

Statistical Considerations:

Sample Size:

The number of subjects is not based on statistical power considerations. If 4 responders are observed out of 10 subjects at a dose level, a 90% confidence interval for the response rate is (0.15, 0.70).

Endpoints:

Primary endpoints of safety will be measured by AE, SAE, ECG, and laboratory abnormalities including safety biomarkers of d-Dimer and TAT.

Secondary endpoint of efficacy is measured by response rate. Secondary endpoints of PK include C_{max}, CLT, AUC(TAU), C_{trough}, AI_AUC, and AI_C_{max}.

Exploratory endpoints include time to response, duration of response, and time to peak response.

Endpoints for the Long Term Extension Period

Primary endpoints of safety for the long-term extension period will be measured by AE, SAE, ECG, and laboratory abnormalities including safety biomarkers of d-Dimer and TAT.

The endpoint of efficacy is measured by response rate.

Analyses:

Demographics and Baseline Characteristics

Frequency distributions of gender and race will be tabulated. Summary statistics for age, body weight, height, and Body Mass Index (BMI) will be tabulated. Prior therapies will be listed and summarized for each dose.

Safety Analyses

All recorded adverse events will be listed and tabulated by system organ class, preferred term and treatment. Vital signs and clinical laboratory test results will be listed and summarized by treatment. Any significant physical examination findings, and clinical laboratory results will be listed. ECG readings will be evaluated by the investigator and abnormalities, if present, will be listed.

Efficacy Analyses

Platelet count and change from baseline will be listed for all treated subjects. Response status will be reported together with time to respond, time to peak response, and duration of response. Response rate will be provided by cohort and treatment phase (response phase or remission phase).

Bleeding score will be listed for each subject. Bleeding events and the number of subjects experiencing any bleeding episode will be summarized by panel.

Pharmacokinetic Analyses

PK parameters will be summarized by treatment. Geometric means and coefficients of variation will be presented for C_{max} (after dose 1 and dose 6), AUC(TAU), CLT, and C_{trough}. Additionally, scatter plots of C_{max} versus dose will be provided to assess the dependency on dose. A statistical analysis using a power model will be applied to assess dose proportionality.

Immunogenicity Analyses

Data from the assessment of immunogenicity markers (anti-BMS-986004 antibodies) will be listed by subjects. In addition, immunogenicity data will be listed separately for all the subjects who have at least one positive assay. Number and frequency of positive subjects will be summarized by dose. Definition of different positivity will be available in the study's Statistical Analysis Plan (SAP).

[REDACTED]

[figure not shown]

[figure not shown]

Other Analyses

Modeling analysis of PK of BMS-986004 will be conducted using a population approach as appropriate and reported separately from the clinical study report.

Long Term Extension Analyses

Similar and appropriate analyses (demographics and baseline characteristics, efficacy analyses, safety analyses, etc) will be conducted for the LTE analysis population when applicable. The analyses for the LTE analysis population are descriptive in nature.

TABLE OF CONTENTS

TITLE PAGE	1
DOCUMENT HISTORY	3
SYNOPSIS.....	4
TABLE OF CONTENTS.....	12
1 INTRODUCTION AND STUDY RATIONALE	16
	16
	16
	17
	18
	18
	19
	19
1.2 Research Hypothesis.....	19
1.3 Objectives(s)	20
1.3.1 Primary Objectives	20
1.3.2 Secondary Objectives.....	20
	20
1.3.4 Long Term Extension Period Objective.....	20
	20
	20
	21
	24
	25
	27
1.5 Overall Risk/Benefit Assessment	27
1.5.1 Potential risks associated with BMS-986004	28
1.5.2 Potential Thromboembolic Effect	28
1.5.3 Potential Immunosuppressive effect	28
1.5.4 Risk of Infusion Reactions.....	29
1.5.5 Other	29
2 ETHICAL CONSIDERATIONS.....	29
2.1 Good Clinical Practice	29
2.2 Institutional Review Board/Independent Ethics Committee.....	30
2.3 Informed Consent.....	30
3 INVESTIGATIONAL PLAN.....	31
3.1 Study Design and Duration.....	31
3.1.1 Intra-subject dose escalation	32
3.1.2 Dose frequency adjustment for responders exceeding 450,000/mm ³ (for non-splenectomized subjects) and 600,000/mm ³ (for splenectomized subjects) platelet count	33
3.1.3 Dose escalation for dose panel and stopping rules	33
3.1.4 Early decision of dose escalation for dose panel.....	36
3.1.5 Long Term Extension.....	38
3.2 Post Study Access to Therapy.....	38

3.3 Study Population.....	38
3.3.1 Inclusion Criteria.....	39
3.3.2 Exclusion Criteria.....	41
3.3.3 Women of Childbearing Potential.....	42
3.3.4 Criteria for Long Term extension.....	42
3.4 [REDACTED].....	43
[REDACTED].....	43
[REDACTED].....	43
[REDACTED].....	43
[REDACTED].....	44
[REDACTED].....	44
[REDACTED].....	44
[REDACTED].....	45
[REDACTED].....	45

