1.5.5 Other

Risks from the PK, PD, and clinical safety phlebotomy procedures are standard and include discomfort at the injection site, bleeding, bruising, and rarely blood clot formation, infection, and fainting. Furthermore, rescue medications are permitted in the study for severe bleeding or wet purpura or if the investigator thinks the patients is at immediate risk. These medications are to be given with the intended purpose of raising platelet counts.

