BMS-986004 will be administered once every 2 weeks as an IV infusion for a total of 7 doses. Four (4) doses will be administered during the Response Phase over a 6 week treatment period. The remaining 3 doses will be administered during the Remission Phase of the study over a 6 week treatment period. Subjects will receive investigational product on Day 1/Week 0, Week 2, Week 4, Week 6, Week 8, Week 10 and Week 12, for a total of 7 doses.

Each dose cohort will enroll 10 new subjects, starting with the respective dose level at Day1/Week 0, regardless of the number of subjects joining a dose cohort because of intra-subject dose escalation.

A new cohort may be opened to treat subjects at a dose lower than 75 mg if at least 6 subjects treated at the 75 mg cohort achieve platelet Response (R) (platelet count $\geq 30,000/\text{mm}^3$ and at least 2-fold increase from the baseline count and absence of bleeding), at the end of response phase (Week 6). The new cohort would follow the same schedule as the other cohorts including intra-subject dose escalation.

The **long term extension (LTE)** period is optional and will include eligible subjects from either cohort 3 or cohort 4 who complete 12 weeks (85-days) of treatment and who achieve a response as defined by at least a doubling of platelets from Short Term Day 1 baseline and a platelet count of $\geq 35,000/\text{mm}^3$ and absence of bleeding and any significant AEs as assessed on D71 or if more recent platelet count is available, based on the most recent platelet count or on the average of the two consecutive most recent platelet counts, whichever is higher. If a subject has platelet counts close to a doubling of platelets and/or between 30,000-35,000 platelets/ mm^3 and absence of bleeding and any significant AEs as assessed on D71, the subject may be considered for the long term extension on a case by case basis, which will involve a review of data from the short term period and which will require approval by the Study Director.

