3.1.1 Intra-subject dose escalation

Intra-subject dose escalation could occur after the subject has completed the Response Phase of the study. The intra-subject dose escalation decision will be based on review of the safety information and platelet count after 4 weeks of treatment. The decision to escalate dose for the subject will be made after evaluating platelet count at Day 50, 7 days after the 4th dose of BMS-986004 has been administered. Subject will receive the next higher dose of BMS-986004 if clinically significant response has not been achieved based on measurement of platelet count on

the last two consecutive counts performed at Day 43 and Day 50, and a favorable safety profile is observed (see Table 3.1.1-1). Clinically significant response is defined as achieving platelet count $\geq 50,000/\text{mm}^3$ with an increase of at least $20,000/\text{mm}^3$ from baseline and absence of bleeding. Subject will then be dosed at the higher dose level for the remainder of the study (Remission Phase), receiving investigational product at that dose on Week 8, Week 10 and Week 12. Active treatment period with BMS-986004, regardless of the dose, may not exceed 12 weeks for any individual subject.

Table 3.1.1-1: Dose Adjustment after Response Phase

Platelet Count at Day 43 and Day 50 (7 days after the 4th dose) (X /mm³)	Action
< 50,000	Dose increase, as indicated by the next dose panel
$\geq 50,000$ with an increase of at least 20,000 from baseline	Dose remains constant on bi-weekly schedule

3.1.2 Dose frequency adjustment for responders exceeding 450,000/mm³ (for non-splenectomized subjects) and 600,000/mm³ (for splenectomized subjects) platelet count

For both the Short Term Study and the Long Term Extension plan, in the event that platelet count exceeds $450,000/\text{mm}^3$ for non-splenectomized subjects and $600,000/\text{mm}^3$ for subjects who underwent splenectomy, in the absence of recent (administered within two weeks) rescue medication, as indicated by the two consecutive platelet count measurements, dosing of the BMS-986004 should be stopped. Subject will remain in the study and platelet counts will be then assessed based on the normal study visit schedule. Dosing of BMS-986004 could be reinitiated only after discussion between Study Director and Investigator if clinically appropriate and dictated by the medical judgment and subject’s safety.

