3.1.5 Long Term Extension

The long term extension (LTE) period is optional and will include eligible subjects who have completed Day 85 (12-weeks of treatment) and who have consented to participate. Eligible subjects [platelet count $\geq 35,000/\text{mm}^3$ with at least a doubling of platelets from short-term baseline, or patients approved by the Study Director on a case by case basis who are close to a two-fold increase from short term baseline and/or have 30,000-35,000 $/\text{mm}^3$ platelets and absence of bleeding and any significant AEs as assessed on D71 or if more recent platelet count is available, based on the most recent platelet count or on the average of the two consecutive most recent platelet counts, whichever is higher], will receive a 1500 mg dose every other week for 24 weeks. Subjects who complete 24 weeks LTE will receive a taper regimen consisting of 1500mg dose on Day 190 and a final dose on Day 218 before entering the 24 week follow-up period (no treatment).

A separate informed consent must be signed by the patients to enter the LTE period.

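### In the readable text, LTE entry and, more narrowly, the Day 43/50 dose-increase rule act on platelet counts with no rescue condition

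*Protocol*

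**What the plan says.** Protocol Section 1.5.5 says that "rescue medications are permitted in the study for severe bleeding or wet purpura or if the investigator thinks the patients is at immediate risk", and adds: "These medications are to be given with the intended purpose of raising platelet counts". Rescue therefore does not require bleeding, and it acts on the variable that drives dosing.

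Two platelet rules take this into account in their own wording:

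- The dosing stop above 450,000/mm³ (600,000/mm³ after splenectomy) in Section 3.1.2 and the synopsis applies "in the absence of recent (administered within two weeks) rescue medication".
- The panel stopping rule in Section 3.1.3 and the synopsis counts a subject only if the "platelet count raise is not attributable to a rescue or concomitant therapy".

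Two platelet rules have no such condition where the text can be read:

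- **Dose increase after the Response Phase** (synopsis, Section 3.1.1, Table 3.1.1-1). The subject goes to the next dose when "clinically significant response has not been achieved based on measurement of platelet count on the last two consecutive counts performed at Day 43" (the second being Day 50), provided that safety is favorable. Clinically significant response means at least 50,000/mm³, a rise of at least 20,000/mm³ and no bleeding. If it is met, the table says "Dose remains constant on bi-weekly schedule".
- **LTE entry** (synopsis, Sections 3.1, 3.1.5, 3.3.4). Subjects from cohorts 3 and 4 need at least 35,000/mm³ and a doubling from Day 1. In 3.1 this is judged on Day 71 or, where a later count exists, "based on the most recent platelet count or on the average of the two consecutive most recent platelet counts, whichever is higher". Those admitted "will receive a 1500 mg dose every other week for 24 weeks", followed by two taper doses.

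SAP 7.5.1 excludes counts from the day of rescue to day +27. It classes them as Not Assessable under both the primary criterion and the clinically significant response criterion.

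**The concern.** The sponsor already treats rescue as something that can make a platelet count misleading, in two dosing rules and in the analysis. The Day 43/50 rule uses the same response criterion as SAP 7.5.1, so one count can hold a subject's dose as a response while the analysis calls it Not Assessable. The LTE rule goes further, because choosing the more favorable of two readings lets a short-lived rise count in the subject's favor.

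What is at stake is in-trial dosing. A subject whose count rose because of rescue could be admitted to prolonged dosing at the highest level of an agent for which Section 1.5.1 lists thromboembolism and infection as potential risks. More mildly, such a subject could stay on an ineffective dose for the rest of the Remission Phase.

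**Working it through.** The plan gives no figure on this point, so there is none to reproduce. The check sets the texts side by side and works out the day windows.

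**1. LTE conditions on the main (non-discretionary) route**

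| Place | Bleeding and significant-AE condition | Higher of latest count and average | Rescue |
|---|---|---|---|
| Synopsis | not stated | not stated | none |
| 3.1 | stated | yes | none |
| 3.1.5 | stated, but can be read as tied to the case-by-case route | yes | none |
| 3.3.4 | stated for the case-by-case route only | yes | none |

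Study Director review applies to near misses: counts close to a doubling and/or between 30,000 and 35,000/mm³.

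**2. How a transient rise passes**

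Table 5.1-2 schedules platelet counts on Days 72, 75, 78 and 85, so counts later than Day 71 exist. Assumed counts: baseline 15,000; rescue on Day 76; Day 78 at 90,000; Day 85 at 20,000.

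- Latest count: 20,000 < 35,000, so it fails.
- Average: (90,000 + 20,000) / 2 = 55,000. This is at least 35,000 and at least 2 × 15,000 = 30,000, so it passes.
- 55,000 is not a near miss, so no review is triggered.

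Both counts fall within two weeks of rescue (2 and 9 days after).

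**3. How far the bleeding score guards against this**

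Inputs: for a count on Day v, the two-week standard of 3.1.2 covers rescue from v−14 to v. The SAP flag covers v−27 to v. Under SAP 7.5.2 each bleeding score runs from the previous visit to the current one; visit days are from Table 5.1-2.

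| Count used | Score covers | Two-week window | Outside score | SAP window | Outside score |
|---|---|---|---|---|---|
| Days 43 and 50, both affected | 29–50 | 36–43 (8 days) | none | 23–43 (21 days) | 23–28 (6 days) |
| Day 71 | 57–71 | 57–71 | none | 44–71 | 44–56 (13 days) |
| Day 78 | 75–78 | 64–78 | 64–74 (11 days) | 51–78 | 51–74 (24 days) |
| Day 85 | 78–85 | 71–85 | 71–77 (7 days) | 58–85 | 58–77 (20 days) |

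If a Day 78 count is used but bleeding is read at Day 71, rescue on Days 72–78 falls outside the score instead.

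For Day 43/50 on the two-week standard, rescue for recorded bleeding is caught. What remains is rescue for immediate risk without recorded bleeding, on about Days 36–43. Example (counts assumed): a 225 mg subject is rescued on Day 38 with zero bleeding scores and has 60,000 on Days 43 and 50. Even with a baseline of 35,000 the rise is 25,000, so the dose stays at 225 mg. The SAP flag runs from Day 38 to Day 65 (38 + 27), so both counts are Not Assessable.

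**4. Size per affected subject**

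- LTE (Table 5.1-3): Day 1, 12 every-other-week visits and 2 taper visits = 15 infusions. LTE Day 1 is short-term Day 85, so 14 are additional: 14 × 1500 mg = 21,000 mg if the LTE is completed.
- Day 43/50: three infusions (Weeks 8, 10 and 12) at the unchanged dose.

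**The case against.** The strongest answer is that the omission lies next to text that cannot be read. Section 3.4, which Section 3.3.2 identifies as holding the restrictions and prohibited treatments, is redacted. SAP Figure 2.1-2 on intra-subject escalation and the protocol schematics are not shown. A reader might infer that the trial has no rescue rule for these decisions. The documents do not support that; they show only that the readable rules carry none.

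Second, the bleeding windows for LTE entry do not by themselves prove an open route. Section 3.1 also requires absence of significant adverse events, and bleeding severe enough to need rescue would plausibly be one. Section 3.3 also asks for qualification on safety. This stands as a partial guard. It does not clearly reach rescue given for immediate risk without bleeding, and the main route in 3.3.4 and the synopsis do not state it.

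Third, the Day 43/50 error is in the cautious direction: the subject keeps the same dose, and 3.1.1 already requires a safety review. This stands, and it is why automatic escalation of rescued subjects would be a trade-off and not a clear improvement.

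Fourth, the two rules that mention rescue concern excessive counts, and the SAP window is an analysis rule. A reader might infer that the SAP contradicts LTE entry. It does not: the SAP reflects amendments through Amendment 02 and has no readable LTE analysis, so its window reaches the LTE only by analogy.

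**Conclusion.** The point holds as a gap in the readable wording, and it is stronger for LTE entry than for Day 43/50.

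For the LTE, a transient rescue-raised count can admit a subject without Study Director review, at up to 14 further infusions (21,000 mg). The bleeding and significant-AE condition of 3.1 is only a partial guard, and the main route in 3.3.4 and the synopsis leave it out. For Day 43/50, on the two-week standard and assuming both counts must qualify, the gap is rescue without recorded bleeding on about Days 36–43; the consequence is three infusions at an unchanged dose.

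The rules apply to the 20 planned subjects in cohorts 3 and 4 (LTE) and the 30 in cohorts 1 to 3 who can escalate. The documents give no rescue rate, so how many would be affected cannot be estimated. The counts in the examples are assumed.

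A reader might also infer that reported efficacy is biased. The documents do not support that for the short-term period, because SAP 7.5.1 removes post-rescue counts when response is derived.

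**What to change.** - **LTE entry (3.1, 3.1.5, 3.3.4):** if the qualifying count, or either count in a qualifying average, falls within two weeks after rescue (the window of 3.1.2), send the subject to the existing case-by-case Study Director review. The sponsor may prefer the four-week SAP window; either will do if it is stated.
- **Main route in 3.3.4 and the synopsis:** carry over the absence of bleeding and of significant adverse events from 3.1, and make plain in 3.1.5 that it applies to both routes.
- **Day 43/50 (3.1.1 and Table 3.1.1-1):** state that a count within two weeks after rescue does not by itself establish clinically significant response. The investigator and Study Director then decide the dose after safety review, with no automatic escalation.
- If Section 3.4 already contains such a rule, a cross-reference is enough.

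The cost is protocol wording. The SAP already provides for a rescue flag (7.5.1) and a listing of rescue medications (7.3.4), and the LTE review step exists. The downside is that a few true responders who received rescue will go to case review.
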